12.3.2 Determination of Full Analysis Set

The full analysis set (FAS) will include all patients who receive VisipaqueTM or saline placebo and have both baseline and post-scan SCr measurements. This population will also be based upon the treatment that the patient is randomized to. The FAS population will be the analysis population for primary, secondary and exploratory analyses.

12.3.3 Determination of Per-Protocol Set

The per-protocol (PP) set will include all patients who receive VisipaqueTM or saline placebo, have both baseline and post-scan SCr measurements, and do not have any major protocol deviations with the potential of impacting data analyses and/or interpretability. This population will be based upon the treatment that the patient is randomized to. Patients in the saline placebo group who receive contrast medium prior to the 48 hour assessments (Follow-up 1) will be excluded from the analysis. Patients in the VisipaqueTM group who receive additional doses of contrast medium prior to the 48 hour assessments (Follow-up 1) will also be excluded from the analysis. Primary, secondary and exploratory analyses will be repeated using the PP set.

12.4 Patient Demographics/Other Baseline Characteristics

A table will be provided with the following information:

- Number of patients enrolled.
- Number of patients included in the FAS.
- Number of patients included in the PP Set.
- Number of patients included in the Safety Population.
- Number of patients withdrawn from the study and the reason for withdrawal.

Demographic information (age, height, weight, and body mass index) will be summarized with descriptive statistics. Gender and race will be summarized by counts and percentages.

Medical histories will be summarized by counts and percentages. Concurrent medications will be recorded and coded by using a standard classification system and grouped by primary and secondary classes, if applicable.

12.5 Study Treatments

For each administration of Visipaque or saline placebo, the volume administered will be summarized. Additionally, hydration pre-scan and within 24 hours post-scan will be summarized in terms of oral, i.v., and total volume of fluids.

12.6 Primary Analysis

12.6.1 Variable

The primary variable is the incidence (proportion) of AKI stage ≥ 1 (by AKIN criteria) at 48 hours after intervention in patients with stage III or stage IV CKD.

12.6.2 Statistical Hypothesis, Model, and Method of Analysis

With P1 defined as the incidence of AKI stage ≥ 1 48 hours after i.v. administration of the iodinated iso-osmolar contrast material iodixanol (Visipaque™ Injection 320 mg-I/mL) and P2 defined as the incidence rate of AKI stage ≥ 1 48 hours after administration of saline placebo, the primary hypothesis to be tested for the primary analysis in the FAS is:

$$H_0: P1 - P2 \geq 0.05$$

$$H_1: P1 - P2 < 0.05$$

A 2-sided 95% confidence interval (CI) for noninferiority testing will be computed for the difference in sample incidence rates for the 2 treatment groups (CECT vs NECT, for the stage III and IV CKD patients combined) by the Miettinen and Nurminen method. If the upper bound of the 95% CI is less than 5%, then the noninferiority of Visipaque™ to the control (saline) will be concluded.

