
Primary Analysis: With P1 defined as the incidence of AKI stage ≥ 1 48 hours after i.v. administration of the iodinated iso-osmolar contrast material iodixanol (Visipaque™ Injection 320 mgI/mL) and P2 defined as the incidence rate of AKI stage ≥ 1 48 hours after administration of saline placebo, the primary hypothesis to be tested for the primary analysis in the FAS is:
		

H₀: P1 - P2 ≥ 0.05
		

H₁: P1 - P2 < 0.05
		

A 2-sided 95% CI for noninferiority testing will be computed for the difference in sample incidence rates for the 2 treatment groups (CECT vs NECT, for the stage III and IV CKD patients combined) by using the Miettinen and Nurminen method. If the upper bound of the 95% confidence interval (CI) is less than 5%, then the noninferiority of Visipaque™ to the control (saline) will be concluded. In addition, the incidence rates and associated 95% CIs for the 2 treatment groups stratified by CKD stage will be reported.
		

Secondary Analyses: The secondary hypothesis to be tested for the secondary endpoints that are proportions is the following:
		

H₀: P1 - P2 ≥ 0.05
		

H₁: P1 - P2 < 0.05
		

The secondary hypotheses will be tested in patients in the FAS with CKD stage III and IV combined. The incidences for the 2 treatment groups (CECT vs NECT) will be compared by using the same statistical method as for the primary analysis.
		

AKI Secondary Endpoint Analyses: The secondary endpoints of the study are:
		

Name of Sponsor/Company: GE Healthcare Ltd. and its Affiliates	Individual Study Table Referring to Part of Dossier in Which the Individual Study or Study Table is Presented: Volume: Reference:	(For National Authority Use Only)
Name of Finished Product: Visipaque™ Injection 320 mgI/mL		
Name of Active Ingredient: Iodixanol		

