8.2 Method of Numbering Patients and Assigning Patients to Treatment Groups

A unique allocation number will be assigned to each patient at a center in successive order of entering the study after signing the informed consent form. No patient may be entered or screened (after failing to meet inclusion/exclusion criteria) into the study more than once. The allocation number will be unique for each patient in the study and will consist of 7 numbers in total: 3 numbers for the center identification and 4 numbers for the patient identification at the center (e.g., 002-0001: first patient in center No. 2).

Once a patient number is assigned, it cannot be reassigned even if the patient is deemed ineligible or withdraws consent. To preserve the scientific integrity of the study, numbers must be assigned in numeric order.

A patient who has given informed consent (or for whom informed consent has been given) but does not fulfil the criteria to participate in the study will receive a patient number and will be logged as a screening failure within the interactive web response system (IWRS)/ interactive

voice response system (IVRS). The patient will also be documented on the Screening Log by using the patient's initials and patient number.

Once patients have completed the screening process they will be enrolled in the study and will be randomly assigned to the NECT group or the CECT group in a 1:1 ratio in accordance with a pre-specified randomization list. Allocation to the enrolment groups, including randomization, will be performed centrally (via the IWRS or IVRS) by the Sponsor or contract research organization (CRO). Randomization will be stratified by CKD stage to achieve a balance of this factor between treatment groups.

No patient will be administered VisipaqueTM or saline placebo before it has been determined that the patient meets the study's inclusion/exclusion criteria and signed and dated informed consent has been obtained.

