^g All blood samples taken prior to dosing and following the scan will be taken from venous blood. Local laboratories will be used for determination of eligibility for the trial and for stratification during randomization. A central laboratory will be utilized for analysis of SCr, cystatin C, and N-GAL collected at the Baseline Visit, Follow-Up 1 and Follow-Up 2 (for patients meeting primary AKIN criteria at Follow-Up 1). Sampling for Follow-Up 1 should occur as close to 48 hours as possible to support the primary endpoint assessment for AKI [ACR 2015], with use of the -6 hour window being preferable to use of the +6 hour window. Urine samples collected for NephroCheck® biomarkers (TIMP-2 and IGFBP-7) for patients where local NephroCheck® testing is available will be taken just before the scan, 4 hours post scan, and at 48 hours post scan.

^h Critical events, including EVAR-related post-baseline events, will be collected from administration to approximately 6 months after administration of Visipaque™ Injection/ saline placebo for assessment by the CEAC.

ⁱ 500 mL of fluids after SCr sampling and before the CT scan to be consumed. 2500 mL of fluids within the 24 hours post-CT period to be consumed. In case of concern about the patient's compliance and/or capability to follow the oral hydration instructions, i.v. administration of isotonic crystalloid solution (saline or bicarbonate) may be considered. Decision on use of i.v. hydration to be made and documented prior to randomization and performed regardless of whether the patient is randomized to the NECT or CECT arm.

^j CT scan according to correct acquisition protocol.

^k Non-contrast duplex ultrasonography will be performed ideally on the same day as NECT imaging and within 2 days of performing the NECT according to correct acquisition protocol.

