12.2 Definitions

CKD staging [National Kidney Foundation 2002] [Kirsztajn 2009]:

Stage I: kidney damage with normal or high GFR (≥ 90 mL/min/1.73 m²)

Stage II: kidney damage with mildly decreased GFR (60-89 mL/min/1.73 m²)

Stage IIIA: moderately reduced kidney function (GFR 45-59 mL/min/1.73 m²)

Stage IIIB: moderately reduced kidney function (GFR 30-44 mL/min/1.73 m²)

Stage IV: severely reduced kidney function (GFR 15-29 mL/min/1.73 m²)

Stage V: very severe or end-stage kidney failure (GFR <15 mL/min/1.73 m²)

AKIN Serum Creatinine Criteria for AKI [AKIN 2015] [Mehta et al. 2007]:

Stage 1: a SCr increase of ≥ 0.3 mg/dL (≥ 26.4 µmol/L) or increase to $\geq 150\%$ to 200% (≥ 1.5 - to 2.0-fold) from baseline within 48 hours

Stage 2: a SCr increase to >200% to 300% (>2.0- to 3-fold) from baseline within 48 hours

Stage 3: a SCr increase to >300% (>3.0-fold) from baseline or SCr \geq 4.0 mg/dL (\geq 354 μ mol/L) with an acute increase of \geq 0.5 mg/dL (\geq 44 μ mol/L) within 48 hours

Standard definition of CIN [[Mehran and Nikolsky 2006](#)]:

Increase in SCr of 0.5 mg/dL or more in the 24 to 72 hours after the CT scan.

Waikar's definitions of AKI [[Waikar and Bonventre 2009](#)]:

Stage 1: 0.3 mg/dL increase in SCr over 24 hours or a 0.5 mg/dL increase in SCr over 48 hours

Stage 2: 0.5 mg/dL increase in SCr over 24 hours or a 1.0 mg/dL increase in SCr over 48 hours

Stage 3: 1.0 mg/dL increase in SCr over 24 hours or a 1.5 mg/dL increase in SCr over 48 hours.

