12.6.4 Supportive Analyses

The incidence rates for the 2 treatment groups stratified by CKD stage and the associated 95% CIs will also be reported. The primary analysis will be repeated in the PP set by CKD stage and for stage III/IV combined.

In addition, a sensitivity analysis will be performed in the FAS adjusting for the covariates of total fluid intake pre-scan and total fluid intake within 24 hours post-scan. This analysis will be done by CKD stage and for stage III/IV combined.

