12.8 Sample Size Calculation

The primary endpoint is the incidence rate (proportion) of AKI stage ≥ 1 (by AKIN SCr criteria) at 48 hours after intervention in patients with stage III or stage IV CKD. With P1 defined as the incidence rate of AKI stage ≥ 1 following i.v. administration of Visipaque™ and P2 defined as the incidence rate of AKI stage ≥ 1 following administration of saline placebo, the sample size estimate is based on the following assumptions and statistical method:

- (1) Both P1 and P2 are 10%
- (2) A noninferiority margin of 5%
- (3) Power of 80% using the 95% CI of P1 – P2
- (4) The score test [Miettinen and Nurminen 1985] with a 1-sided 0.025 significance level is employed

A sample size of 1164 randomized patients (582 per treatment group) in the FAS will provide 80% power to demonstrate noninferiority of the proportion of AKI stage ≥ 1 (by AKIN criteria) in patients receiving Visipaque™ Injection 320 mgI/mL as compared with patients receiving the saline placebo.

To compensate for a screen failure rate of approximately 15%, approximately 1370 patients will be screened.

It is expected that the number of patients who are excluded from the PP set will be small, resulting in minimal loss of statistical power. However, the number of patients excluded from

the PP set will be monitored and the sample size may be increased as needed to maintain adequate statistical power to repeat the primary analysis in the PP set.

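### Randomization is stratified by CKD stage but the primary noninferiority interval pools the stages; a stage-stratified interval would add a little precision at no cost

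*Combined protocol and SAP*

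**What the plan says.** - **Randomization (section 8.2):** "Randomization will be stratified by CKD stage to achieve a balance of this factor between treatment groups". No other stratification factor is named. The stage used for allocation comes from local results (section 9, Table 1, footnote g): "Local laboratories will be used for determination of eligibility for the trial and for stratification during randomization".
- **Primary analysis (section 12.6.2):** a two-sided 95% interval for the difference in incidence is computed "for the stage III and IV CKD patients combined) by the Miettinen and Nurminen method", and noninferiority is concluded if its upper bound is below 5%. The synopsis has the same instruction: "for the stage III and IV CKD patients combined) by using the Miettinen and Nurminen method".
- **Supportive analyses (section 12.6.4):** "The incidence rates for the 2 treatment groups stratified by CKD stage and the associated 95% CIs will also be reported". Here stratified means reported separately for each stage. The per-protocol repeat is done by stage and combined. The one adjusted sensitivity analysis uses fluid intake before and after the scan, not stage.
- **Sample size (section 12.8):** a single rate of 10% in both arms, a 5-point margin and 80% power, with 582 per arm. On the test: "The score test [Miettinen and Nurminen 1985] with a 1-sided 0.025 significance level is employed".

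**The concern.** When randomization is balanced within a prognostic factor, the variation between its levels no longer contributes to the error of the treatment difference. A single-table interval still counts that variation, so it comes out slightly too wide. An interval stratified by the same factor removes it.

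Stage could well be prognostic here. AKIN stage 1 can be met by "a SCr increase of ≥ 0.3 mg/dL" (section 12.2), which is a smaller relative change when baseline creatinine is higher. The plan nevertheless gives no combined estimate that uses the one factor it chose to balance.

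What is at stake is the width of the interval that decides the trial. The validity of the claim is not at stake, and pooling does not make a false noninferiority conclusion easier.

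**Working it through.** **1. The plan's own figure.** The inputs from section 12.8 are 10% in both arms, margin 0.05, one-sided 0.025 and 80% power. The restricted maximum-likelihood rates at a difference of 0.05 are 0.1303 and 0.0803.

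- Null variance term: 0.1303 × 0.8697 + 0.0803 × 0.9197 = 0.187. Alternative: 2 × 0.10 × 0.90 = 0.18.
- n per arm = [(1.96 × √0.187 + 0.842 × √0.18) / 0.05]² ≈ 581, against 582 in the plan.
- Exact enumeration of the pooled Miettinen-Nurminen test at 582 per arm gives power 80.5%, and one-sided error 2.47% at 15% versus 10%.

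The stated sample size is reproduced.

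**2. Variance removed by stratifying.** Let s be the stage IV share, and let p3 and p4 be the AKI rates by stage, equal in both arms and averaging 10%. For rate ratio R, p3 = 0.10 / (1 − s + sR) and p4 = R × p3.

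- Variance cut = s(1 − s)(p4 − p3)² / (0.10 × 0.90).
- Equivalent patients = cut × 1164.
- Pooled half-width = 1.96 × √(0.18/582) = 3.45 points. The stratified half-width is this times √(1 − cut).

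Example with R = 2 and s = 0.10: p3 = 9.1%, p4 = 18.2%, cut = 0.09 × 0.0909² / 0.09 = 0.83%, and 0.0083 × 1164 ≈ 10 patients.

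The documents give neither s nor R. The ranges below are assumptions, and R = 3.7 is simply an upper extreme with no source in the documents.

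| R (s = 10 to 30%) | Variance cut | Patients | Half-width narrower by (points) |
|---|---|---|---|
| 1 | 0 | 0 | 0 |
| 2 | 0.8–1.4% | 10–16 | 0.014–0.024 |
| 3 | 2.8–3.7% | 32–42 | 0.05–0.06 |
| 3.7 | 4.5–5.5% | 53–64 | 0.08–0.10 |

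**3. Simulated operating characteristics.** At least 300,000 trials were run per scenario, with 582 per arm and arms balanced within stage. With that balance, Mantel-Haenszel weights equal sample-size weights. Results at s = 0.20:

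| R | Power, pooled | Power, stratified |
|---|---|---|
| 1 | 80.5% | 80.5% |
| 2 | 80.7% | 80.8% |
| 3 | 81.0% | 81.6% |
| 3.7 | 81.3% | 82.2% |

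Over shares of 10 to 30%, the gain is 0.10 to 0.15 points at R = 2, 0.5 to 0.6 at R = 3 and 0.8 to 0.9 at R = 3.7. With a true difference of 0.05 in both stages, one-sided error is 2.2 to 2.5% pooled and 2.4 to 2.5% stratified. Stratifying brings the error closer to its nominal level without a material excess.

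**The case against.** The strongest reply is that nothing is broken. One hypothesis, one pooled interval, one 10% rate and one score test fit together, and the blinded re-estimation in section 12.8 also works on the overall rate. Power is met with the pooled test, and by-stage results are planned. That is correct, and it is why the point is optional.

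The evidence that stage is prognostic is also thin. The background (section 4) cites two retrospective studies in which risk rose as renal function fell, but those concern the effect of contrast, not AKI rates in both arms. Other studies cited there question causation. The gain could therefore be nil. That stands, but stratifying costs essentially nothing in that case: at R = 1 the power is unchanged.

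Two further points stand. The protocol defers details to a SAP, and the available text has no separate SAP sections, so the absence of a stratified difference is confirmed only for that text. And section 12.7.1 carries the primary method over to the secondary proportions and to the binary morbidity and mortality outcomes. A change in section 12.6.2 would reach those too, including rare events with possibly sparse stage IV cells, unless the text says otherwise.

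**Conclusion.** The point holds as a free but small improvement. Analysing by the factor used for randomization narrows the deciding interval by between 0 and 0.10 points from 3.45, and raises power by 0 to 0.9 points. This assumes 10% AKI overall, a stage IV share of 10 to 30% and a rate ratio between 1 and 3.7, the same in both arms. At a ratio of 2 the gain is barely visible.

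Pooled power stays at 80.5 to 81.3% across these scenarios, provided all 582 per arm reach the full analysis set. The pooled conclusion would be valid and slightly conservative, so neither the sample size nor the margin is in question.

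**What to change.** In section 12.6.2, the synopsis and the SAP, define the primary risk difference and 95% interval as a Miettinen-Nurminen interval stratified by CKD stage as randomized (the local-laboratory stage used for allocation). Name Mantel-Haenszel weights and keep the same 5% rule. Report the pooled interval as a sensitivity analysis.

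State in section 12.7.1 whether the secondary AKI endpoints and the morbidity and mortality outcomes follow the stratified method or stay pooled. Leaving the rare outcomes pooled is acceptable.

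If the sponsor prefers the pooled interval as primary, add the stratified one to section 12.6.4 as a named sensitivity analysis.

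The cost is a sentence or so in each of these places, with no new data and no change to sample size or margin. Settle it before any comparison by arm is seen, so that the choice cannot look driven by the data.

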12.6.3 Handling of Missing Values/Censoring/Discontinuations

Missing values will not be imputed, and only observed values will be used in data analyses and reports, unless otherwise specified in the Statistical Analysis Plan (SAP).

12.6.4 Supportive Analyses

The incidence rates for the 2 treatment groups stratified by CKD stage and the associated 95% CIs will also be reported. The primary analysis will be repeated in the PP set by CKD stage and for stage III/IV combined.

In addition, a sensitivity analysis will be performed in the FAS adjusting for the covariates of total fluid intake pre-scan and total fluid intake within 24 hours post-scan. This analysis will be done by CKD stage and for stage III/IV combined.

12.7 Secondary Analyses

12.7.1 Secondary Variables and Analyses

The secondary hypothesis to be tested for the secondary endpoints that are proportions is the following:

$$H_0: P_1 - P_2 \geq 0.05$$

$$H_1: P_1 - P_2 < 0.05$$

The secondary hypotheses will be tested in patients in the FAS with CKD stage III and IV combined. The incidences for the 2 treatment groups (CECT vs NECT) will be compared by using the same statistical method as for the primary analysis.

AKI Secondary Endpoint Analyses:

The secondary endpoints of the study are:

Incidence of AKI stage ≥ 2 (by AKIN SCr criteria [\[AKIN 2015\]](#)[\[Mehta et al. 2007\]](#)) following an i.v. injection of iodinated iso-osmolar contrast material iodixanol (Visipaque™ Injection 320 mg I/mL) or saline in patients with CKD stage III or IV. This analysis will be performed for the FAS assessed at 48 hours post-baseline (Follow-up 1).

Incidence of AKI (by standard definition of CIN [[Mehran and Nikolsky 2006](#)]) following an i.v. injection of iodinated iso-osmolar contrast material iodixanol (VisipaqueTM Injection 320 mg I/mL) or saline in patients with CKD stage III or IV. This analysis will be performed for the FAS assessed at 48 hours post-baseline (Follow-up 1).

Incidence of AKI stage ≥ 2 (by Waikar criteria [[Waikar and Bonventre 2009](#)]) following i.v. administration of iodinated iso-osmolar contrast material iodixanol (VisipaqueTM Injection 320 mg I/mL) or saline in patients with CKD stage III or IV. This analysis will be performed for the FAS assessed at 48 hours post-baseline (Follow-up 1).

In order to control the false positive rate at a one-sided 0.025 level across the testing of the secondary endpoints, the above endpoints will be tested hierarchically in the order given above. Each endpoint will be tested at a one-sided 0.025 level of significance; when a statistical test for a given endpoint fails to reach statistical significance in the appropriate direction, testing on all remaining secondary endpoints in the hierarchy will cease and the study will be considered successful on all secondary endpoints up to that point.

Secondary endpoint analyses will be repeated in the FAS for CKD stage III and IV separately and in the PP set by CKD stage and for stage III/IV combined.

Other Secondary Endpoint Analyses:

Other secondary endpoint analyses will be conducted using the safety population for stage III/IV combined. In addition, these summaries and analyses will be repeated for the stage III CKD subgroup and the stage IV CKD subgroup separately.

Mortality and morbidity events:

- All-cause death assessed at 6 months (Follow-up 3).
- Critical events (including EVAR-related post-baseline events as adjudicated by the CEAC) assessed at 6 months (Follow-up 3).
- Incidence rate of hospitalization due to renal failure assessed at 6 months (Follow-up 3).
- Incidence of requirement for renal replacement therapy (i.e., renal transplant, dialysis, or hemofiltration/ultrafiltration) assessed at 6 months (Follow-up 3).
- Incidence of the composite of death and hospitalization events due to renal failure assessed at 6 months (Follow-up 3).
- Hospital length of stay (LOS) in days assessed at 6 months (Follow-up 3).
- Incidence rate of patients with $\geq 30\%$ reduction in eGFR at 48 hours compared to baseline.
- Other criteria defined by the CEAC.

Among the morbidity and mortality events, binary variables will be analyzed using the noninferiority test for proportions described above. Hospital LOS will be summarized descriptively by arm.

[figure not shown]
Image quality/diagnostic confidence analyses:

- Image quality/diagnostic confidence will be rated on a scale of 1 to 5. The frequency distribution of image-quality/diagnostic confidence ratings will be summarized for each type of imaging procedure in each treatment arm. Thus, there will be 2 separate summaries of image quality/diagnostic confidence ratings, CECT and NECT plus non-contrast duplex ultrasonography images. Both by-reader and majority-read analyses will be performed for each summarization.
- The image-quality/diagnostic confidence ratings will be analyzed based on individual scores and will also be dichotomized as evaluable (rating of 3 to 5) or nonevaluable (rating of 1 or 2). The frequency distribution of evaluable vs nonevaluable image quality/diagnostic confidence ratings will be summarized for each treatment group. Thus, there will be 2 separate summaries of image quality/diagnostic confidence ratings: CECT and NECT plus non-contrast duplex ultrasonography. Both by-reader and majority-read analyses will be performed for each summarization.

No statistical comparisons between the CECT images and NECT images plus duplex ultrasonography images will be made.

For a randomly selected subset of 5% of the patients (N=29 in each arm), the images will undergo a second blinded visual assessment by the same reader. Intra-reader (within-reader) agreement for these blinded visual image assessments will be measured by percentage agreement. A percentage agreement with an exact 95% CI will be determined for each reader comparison and all readers for subjects with re-reads of images. In cases where images are re-read, it is the result of the first read that is to be included in the image quality/diagnostic confidence summaries.

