
 Incidence of AKI stage ≥ 2 (by AKIN SCr criteria [AKIN 2015] [Mehta et al. 2007]) following an i.v. injection of iodinated iso-osmolar contrast material iodixanol (Visipaque™ Injection 320 mg I/mL) or saline in patients with CKD stage III or IV. This analysis will be performed for the FAS assessed at 48 hours post-baseline (Follow-up 1). Incidence of AKI (by standard definition of CIN [Mehran and Nikolsky 2006]) following an i.v. injection of iodinated iso-osmolar contrast material iodixanol (Visipaque™ Injection 320 mg I/mL) or saline in patients with CKD stage III or IV. This analysis will be performed for the FAS assessed at 48 hours post-baseline (Follow-up 1). Incidence of AKI stage ≥ 2 (by Waikar criteria [Waikar and Bonventre 2009]) following i.v. administration of iodinated iso-osmolar contrast material iodixanol (Visipaque™ Injection 320 mg I/mL) or saline in patients with CKD stage III or IV. This analysis will be performed for the FAS assessed at 48 hours post-baseline (Follow-up 1). 
In order to control the false positive rate at a one-sided 0.025 level across the testing of the secondary endpoints, the above endpoints will be tested hierarchically in the order given above. Each endpoint will be tested at a one-sided 0.025 level of significance; when a statistical test for a given endpoint fails to reach statistical significance in the appropriate direction, testing on all remaining secondary endpoints in the hierarchy will cease and the study will be considered successful on all secondary endpoints up to that point.
 
Other Secondary Endpoint Analyses:
 
Mortality and morbidity:
 
 All-cause death assessed at 6 months (Follow-up 3). Critical events (including EVAR-related post-baseline events) assessed at 6 months (Follow-up 3). Incidence rate of hospitalization due to renal failure assessed at 6 months (Follow-up 3). Incidence of requirement for renal replacement therapy (i.e., renal transplant, dialysis, or hemofiltration/ultrafiltration) assessed at 6 months (Follow-up 3). Incidence of the composite of death and hospitalization events due to renal failure assessed at 6 months (Follow-up 3). Hospital length of stay (LOS) in days assessed at 6 months (Follow-up 3). Incidence rate of patients with $\geq 30\%$ reduction in eGFR at 48 hours compared to baseline. Other criteria defined by the CEAC. 
Among the mortality and morbidity events, binary variables will be analyzed using the noninferiority test for proportions described above. Hospital LOS will be summarized descriptively by arm.
 
Image quality/diagnostic confidence will be rated on a scale of 1 to 5. The frequency distribution of image-quality/diagnostic confidence ratings will be summarized for each type of imaging procedure in each treatment arm. Thus, there will be 2 separate summaries of image quality/diagnostic confidence ratings, CECT and NECT plus non-contrast duplex ultrasonography images. Both by-reader and majority-read analyses will be performed for each summarization.
 
The image-quality/diagnostic confidence ratings will be analyzed based on individual scores and will also be dichotomized as evaluable (rating of 3 to 5) or nonevaluable (rating of 1 or 2). The frequency distribution of evaluable vs. nonevaluable image quality/diagnostic confidence ratings will be summarized for each treatment group. Thus, there will be 2 separate summaries of image quality/diagnostic confidence ratings: CECT and NECT plus non-contrast duplex ultrasonography. Both by-reader and majority-read analyses will be performed for each summarization.
 
In addition, the above analyses will be repeated for the stage III CKD subgroup and the stage IV CKD subgroup separately.
		

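### The protocol states no condition that the primary must succeed before the AKI secondary hierarchy is tested, so primary and hierarchy form two separate one-sided 0.025 families

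*Combined protocol and SAP*

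**What the plan says.** Section 12.6.2 tests AKI stage ≥1 at 48 hours against a 5-point margin, using the Miettinen-Nurminen two-sided 95% interval. The conclusion is read from the upper limit: "If the upper bound of the 95% CI is less than 5%, then the noninferiority of" contrast to saline is concluded.

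Section 12.7.1 carries the same margin and method over to other outcomes: "The secondary hypothesis to be tested for the secondary endpoints that are proportions is the following", followed by the 5-point null. Three AKI endpoints are then ordered: AKIN stage ≥2, the standard CIN definition, and Waikar stage ≥2. The stated aim is "In order to control the false positive rate at a one-sided 0.025 level across the testing of the secondary endpoints". Each is tested at one-sided 0.025. A failure stops the later ones, and "the study will be considered successful on all secondary endpoints up to that point". The synopsis has the same scheme. The only stopping event named is failure of an earlier secondary.

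The mortality and morbidity outcomes are listed separately, outside this order. Section 12.7.1 says "Among the morbidity and mortality events, binary variables will be analyzed using the noninferiority test for proportions described above", and the synopsis agrees. Image quality is not tested: "No statistical comparisons between the CECT images and NECT images plus duplex ultrasonography images will be made".

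**The concern.** A fixed-order secondary hierarchy is usually entered only after the primary succeeds, so that primary and secondaries share one error rate. Here the primary has its own one-sided 0.025, the hierarchy has another, and no sentence links them. Followed literally, the protocol allows a report in which contrast fails noninferiority on AKI stage ≥1 while the study is declared successful on AKIN stage ≥2, CIN and Waikar stage ≥2. Section 5 presents these secondaries as demonstrations of safety, so such a report would carry weight. What is at stake is which claims the trial may make after a failed primary, and the joint chance of a false one.

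**Working it through.** **Inputs.** Sections 12.6.2, 12.7.1 and 12.8 give 582 per arm, a 5-point margin, the Miettinen-Nurminen score test, one-sided 0.025, and 10% in both arms for the primary. The documents give no rates for the AKI secondaries, so those below are assumptions. AKIN stage ≥2 is a subset of stage ≥1 by the definitions in section 12.2. In step 5 the other AKI endpoints are also treated as nested.

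**1. Reproduce the plan's sample size.** With rates 10%/10% and margin 0.05, the restricted estimates under the null are 0.1303 and 0.0803.

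- s0 = √(0.1303×0.8697 + 0.0803×0.9197) = 0.4326
- s1 = √(2×0.10×0.90) = 0.4243
- n = [(1.960×0.4326 + 0.8416×0.4243)/0.05]² ≈ 581 per arm, against 582 planned

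Exact enumeration at 582 per arm gives 80.5% power, so the primary fails in 19.5% of trials when the arms are equal. At 10% vs 15% the test passes in 2.47%. The plan's figures hold.

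**2. Joint error, both nulls true at the margin.** Take the primary at 10% vs 15% and AKIN stage ≥2 at 1% vs 6%. The two test statistics are correlated through nesting:

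- covariance = 0.06×0.85 + 0.01×0.90 = 0.060
- variances = 0.15×0.85 + 0.10×0.90 = 0.2175, and 0.06×0.94 + 0.01×0.99 = 0.0663
- correlation = 0.060/√(0.2175×0.0663) = 0.50

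The bivariate normal then gives 4.5% for at least one false claim. Simulating the actual test (1,000,000 trials) gives a false primary pass in 2.49%, a false secondary pass in 2.22%, and a secondary pass with the primary failed in 1.80%. The total is 2.49% + 1.80% = 4.29%. At 2% vs 7% it is 4.28%, and at 3% vs 8% it is 4.18%. Repeat simulations gave 4.2% to 4.3% in all three cases. For reference, two independent tests would give 1 − 0.975² = 4.94%.

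**3. Away from that point.** At 10% vs 17% on the primary, with AKIN stage ≥2 still at 1% vs 6%, the primary passes falsely in about 0.15% of trials and the joint error is about 2.3%. If the true AKIN stage ≥2 excess is below 5 points, passing that test is a correct statement, and only the primary's 2.5% remains.

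**4. With a gate.** Primary and hierarchy become one fixed sequence, and the joint error is at most 2.5%.

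**5. What the gate costs.** Under 10%/10% with equal rates in both arms, assume AKIN stage ≥2 1%, Waikar stage ≥2 1.5% and CIN 3%. The primary then fails and all three secondaries pass in 19.2% of trials. With 1%, 2% and 5%, this is 16.8%. These passes are correct: they show how often the situation arises, not error.

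**6. Reading only the upper limit.** With 6 control events and 23 contrast events out of 582 each, the 95% interval is 1.2 to 4.9 points. It lies wholly above zero and still meets the noninferiority rule. At 582 per arm this overlap is possible only when the control arm has 0 to 19 events (at most 19/582 = 3.3%).

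**The case against.** The strongest reply is that the plan keeps its promise. It undertakes to control error across the secondaries, and the fixed order does so. A 2.5% rate across primary plus secondaries is a benchmark brought by the reader, so a reader who infers that the plan contradicts itself goes too far. This stands.

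The 4.3% also belongs to a narrow case. In every scenario of step 2 the whole 5-point excess consists of creatinine more than doubling, with stage 1 AKI equal in both arms (for example 9% vs 9%). That stands, so the figure must be given with its condition.

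The gate has a price: under equal rates it would block correct secondary conclusions in roughly one trial in six to one in five. That stands too, and the sponsor should see the number.

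A reader might infer that the shared 5-point margin and the upper-limit rule make the secondary and mortality tests unsound. The documents do not support that. The test holds its level (1% vs 6% passes in 2.2%), the lower limit is already part of the two-sided interval, and the outcome rates that would make the overlap matter are not given. Requiring a statement of significant harm whenever the lower limit exceeds zero would itself add unadjusted claims. Over nine outcomes (three AKI secondaries and six named binary events), if independent and tested at 2.5% each, the chance of at least one is 1 − 0.975⁹ ≈ 20%.

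Finally, the protocol defers some details to a SAP, and no separate SAP text was available. A gate stated only there would not be visible. The testing scheme in 12.7.1 is not among the matters deferred.

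**Conclusion.** The gap is real but limited. The protocol states no gate between the primary and the AKI hierarchy, and as written it allows success on AKI secondaries after a failed primary. The joint chance of a false noninferiority claim is about 4.2% to 4.3% at 582 per arm when both true excesses equal 5 points, on assumed secondary rates. It is close to 2.5% when only one null holds or the primary excess is clearly larger. The mortality and morbidity tests are outside the hierarchy, carry no success label and are not counted in this figure. The primary analysis and sample size are unaffected. This is a cheap improvement to what the trial may claim. Confidence is medium, because a separate SAP could contain the gate.

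**What to change.** Add to section 12.7.1 and the synopsis: *The AKI secondary endpoints are tested in the stated order only if noninferiority is shown on the primary endpoint; otherwise they are reported as estimates with 95% CIs.* If a separate SAP already has this condition, carry it into both places.

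For the secondary and the mortality and morbidity tests, report counts by arm and the full two-sided 95% interval for the difference beside any noninferiority statement. Note descriptively when the interval lies wholly above zero, and make no unadjusted significance claim.

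The cost is one amendment under section 13.1 and no new data. Because the study is not blinded (section 8.4), the change should be made before anyone reviews data by arm. The statistical price is the loss of formal AKI secondary claims when the primary fails. Under 10%/10% that is about 19.5% of trials. In most of these, about 17% to 19% of all trials on the assumed rates, the secondaries would have passed correctly.
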